4. Determine the potential alterations in VO₂max, anaerobic threshold, jump force, acceleration, step speed, and race time in college athletes, following a 12-week exercise program aimed at correcting two foot structural types (high or low). This investigation will use Ergospirometry and a 3D motion kinematics assessment system to evaluate possible improvements in sports performance resulting from the exercise program.

Methodology:

Design and Sample: An observational study design was employed to assess the impact of foot structural types on postural stability, activity of core stabilizing muscles, maximum oxygen consumption (VO₂max), anaerobic threshold, and lower limb performance in male college athletes over 18 years old from the University of Magdalena, participating in various sports modalities such as rugby, soccer, basketball, volleyball, tennis, table tennis, karate, and cheerleading. For evaluating the effects of a corrective exercise program targeting high or low foot posture alterations on the same variables, an experimental design was used. Stratified random sampling was employed for convenience, and 35 participants with low medial arch, 32 with high arch, and 36 with neutral arch were selected for the observational studies. For the experimental studies, 33, 31, and 33 participants were selected, respectively, from a pool of 230 candidate athletes. G Power 3.1.9.7 software was used to determine the appropriate sample size, considering three independent groups, an alpha level set at 0.05, a power (1-β) of 0.80, and an effect size (f) of 0.40.

Foot Type Evaluation: The Foot Arch Index, which determines the medial arch height by measuring the ratio between the midfoot area and the total foot area (excluding toes), was used to evaluate the foot type. An index less than 0.21 indicated a high-arched foot, an index greater than 0.26 indicated a flat foot, and an index between 0.21 and 0.26 was considered a "neutral" arch. Participants' footprints were obtained using a washable ink pad, and analysis software was used to calculate the Foot Arch Index.

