Statistical Analysis: Data were reported as mean \pm standard deviation and analyzed using IBM SPSS Statistics (version 21, IBM Corp., NY, USA). The normality of each variable for different foot types (low, high, or neutral) was checked using the Shapiro-Wilk test. The significance of variables such as age, weight, height, and muscle/fat percentages among the three foot types was evaluated using ANOVA if the variables followed a normal distribution, or the Kruskal-Wallis test if they did not. For descriptive studies, ANOVA was used for normally distributed dependent variables or Kruskal-Wallis for non-normally distributed variables. Levene's test was used to assess homogeneity of variances. Post-hoc analysis with Bonferroni correction was performed to determine differences between groups. Pearson's or Spearman's correlation was used to assess the relationship between variables. For experimental studies, the effects of exercise on dependent variables were assessed using repeated-measures ANOVA or Friedman's test. Levene's test was used for variance homogeneity. Post-hoc analysis with Tukey correction was conducted to assess pre-post exercise significances of dependent variables. Eta-squared (η^2_p) or Kendall's W concordance coefficient was used to evaluate the effect size of the exercise program on foot types. The significance level for both studies was set at $p \leq 0.05$.

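### Efficiency point: a step-down rule would hold the same 5% family error as Bonferroni for the three arch comparisons and identify more of the pairs that differ

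*Combined protocol and SAP*

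**What the plan says.** Everything here is in the combined protocol and SAP.

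- **Statistical Analysis, descriptive studies.** The overall comparison is "ANOVA was used for normally distributed dependent variables or Kruskal-Wallis for non-normally distributed variables". It is followed by: "Post-hoc analysis with Bonferroni correction was performed to determine differences between groups". On variances, the plan says "Levene's test was used to assess homogeneity of variances" but names no test to use if they differ. "The significance level for both studies was set at" p ≤ 0.05.
- **Methodology, Design and Sample.** "35 participants with low medial arch, 32 with high arch, and 36 with neutral arch were selected for the observational studies". Sample size was set "considering three independent groups, an alpha level set at 0.05, a power (1-β) of 0.80, and an effect size (f) of 0.40". The pattern of means behind f = 0.40 is not given.

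The plan gives no reason for choosing Bonferroni. It does not say whether pairs are tested only after a significant overall test, although the term post-hoc suggests it. It does not name the pairwise test for the Kruskal-Wallis branch. Results are reported as mean and SD, and no simultaneous confidence intervals are planned.

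**The concern.** Specific Objectives 1 and 2 ask how low, high and neutral arches differ. The overall test says only that some difference exists; the pairwise tests say where it lies. Bonferroni allows for three true pairwise nulls at every step. With three groups that is more than logic requires: once one pair is known to differ, at most one of the other two nulls can still be true. Keeping 0.05/3 for all three pairs therefore gives up power on the question the objectives ask. At stake are true differences between arch types reported as non-significant. The validity of the results is not at stake.

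**Working it through.** **Inputs.** From the plan: three groups; n = 35 low, 32 high, 36 neutral (total 103); alpha 0.05; f = 0.40. Assumed: pairwise tests are two-sided; patterns of means and SD ratios are as stated below, because the plan gives none.

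**The plan's own figures.** One-way ANOVA with f = 0.40, alpha 0.05 and power 0.80 needs N = 66 (22 per group). The plan does not state the N its calculation produced. The 103 selected exceed 66 and give 95.7% power for the overall F test (noncentrality 103 × 0.40² = 16.48). There is no shortfall, and the point below does not depend on this.

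**Why step-down is enough with three groups.**
1. If all three pairwise nulls are true, Shaffer's rule makes an error only if the smallest p-value is at most 0.05/3. That has probability at most 5%, exactly as for Bonferroni.
2. If two pairwise nulls are true, the third is true as well, so this is case 1.
3. If exactly one null is true, an error needs that single pair to reach p ≤ 0.05, so again at most 5%.

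The family error is therefore at most 5% per variable. Every Bonferroni rejection is also a Shaffer rejection.

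**Effect sizes implied by f = 0.40.**
- One group differing by d: f = d√(2/9), so d = 0.40/0.471 = 0.849 SD.
- Evenly spaced means, step δ: f = δ√(2/3), so δ = 0.40/0.816 = 0.490 SD, and the extreme pair differs by 0.980 SD.
- One group differing by 0.66 SD corresponds to f = 0.66 × 0.471 = 0.31.

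**Hand check, low v neutral, evenly spaced.** The standard error in SD units is √(1/35 + 1/36) = 0.237, so the noncentrality is 0.490/0.237 = 2.06. The two-sided critical t on 100 df is 2.43 at 0.0167 and 1.98 at 0.05. Approximate power is Φ(2.06 − 2.43) = 36% and Φ(2.06 − 1.98) = 53%.

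**Simulation at 35/36/32, normal errors, equal SDs.**

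| Pattern | Pair | Bonferroni | Shaffer |
|---|---|---|---|
| Evenly spaced, f = 0.40 | adjacent pairs | 34-36% | 51-53% |
| Evenly spaced, f = 0.40 | extreme pair | about 94% | about 95% |
| One group differing, f = 0.40 | each true pair | 85-87% | 91-92% |
| One group differing by 0.66 SD | each true pair | 61-64% | 69-71% |

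The chance of at least one rejection is identical under the two rules, because both start by comparing the smallest p-value with 0.05/3.

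**Error rates.** Under equal means, Bonferroni has a family error of 4.35%, and Shaffer has the same by construction. With one group far from two equal groups, the null pair is rejected 1.6-1.7% of the time under Bonferroni and about 5% under Shaffer.

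**Unequal variances (SD ratios assumed).** With one group far off and SD ratios of 1.5 to 2, testing the null pair at 0.05 with a pooled SD gives 7.7-9.2% false positives, against 3.1-4.0% for Bonferroni with the same pooled SD. With Welch pairs it stays at about 5%. At equal SDs, Welch pairs cost about a point of power or less.

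**Rank branch.** Each Mann-Whitney test uses only its own two groups, so the argument above carries over for nulls of identical distributions. In simulations of pairs tested at 0.05 after a significant Kruskal-Wallis test, Mann-Whitney pairs held at 4.7-5.0%, while Dunn pairs on joint ranks reached 5.9% in one scenario. The pairwise test should therefore be named.

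**The case against.** The strongest reply is that Bonferroni is valid, familiar and needs no gate, so choosing another rule is a matter of preference. Much of this stands. No planned result is invalid, and no objective becomes unanswerable. At the planned f = 0.40 with one group differing, Bonferroni already exceeds 80% power for each true pair, and the gain is only about 5-6 points. The large gain is confined to adjacent pairs under evenly spaced means; the extreme pair gains about 1 point.

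The slack in Bonferroni also has some value. When another group truly differs, the null-pair error per variable rises from about 1.7% to the nominal 5% under step-down. The plan has many outcomes and no correction across them. Neither rule addresses that.

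A reader might go further and infer that, because an overall test comes first, the Bonferroni step buys nothing and the pairs can simply be tested at 0.05. For three groups with equal variances, that gated rule does control the family error (5.0% under equal means, 4.9-5.0% with one group far off). But the plan does not state the gate, and ungated pairs at 0.05 give 12.1%. The plan also names no unequal-variance test, and with a pooled SD the gated rule reaches the 7.7-9.2% shown above. Dropping the correction in the plan as written could therefore turn a conservative procedure into one above 5%. Step-down with Welch pairs avoids both problems.

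**Conclusion.** The point holds as a cheap improvement, not as an error in the plan. For the three arch comparisons, Shaffer's step-down rule gives the same 5% family error per variable and is never less powerful. The gain ranges from about 1 point (extreme pair) to about 17 points (adjacent pairs under evenly spaced means at f = 0.40), with roughly 5-8 points when one group differs. It lies wholly in identifying which arch types differ.

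These sizes rest on assumed patterns of means, normal errors and equal SDs. The error-control argument does not depend on the pattern of means, but it does require pairwise tests that are themselves valid, hence Welch or Mann-Whitney. The documents do not support a claim that Bonferroni is wrong here, or that it protects against nothing.

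**What to change.** Replace the Bonferroni sentence for the descriptive studies with:

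*The three pairwise comparisons use Shaffer's step-down procedure: if the smallest of the three p-values is at most 0.05/3, the other two pairs are each tested at 0.05; pairs are compared with Welch t-tests after ANOVA, or with Mann-Whitney tests in the Kruskal-Wallis branch.*

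The overall test is still reported but is not needed as a gate. Testing pairs at 0.05 after a significant overall test is a usable alternative only if the gate is written into the plan and variances are equal.

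**Cost.** One sentence and no extra data. The rule can be applied by hand to three p-values.

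**Downsides.**
- There are no simple matching simultaneous intervals. None are planned, so any pairwise 95% confidence intervals should be labelled unadjusted.
- The null-pair error rises to the nominal 5% when another group truly differs.
- Multiplicity across outcomes stays open and needs its own statement.

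The analysis section is written in the past tense. If results have already been seen, report the change as made after the fact and show the Bonferroni results beside it.

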The measurements were performed during the general preparation stage of each sports semester, with no changes in diet and approximately two hours after the main meal of the day. To evaluate aerobic capacity (VO₂max) and anaerobic threshold, participants underwent an incremental treadmill test. The test began with a 3-minute warm-up at a speed of 4.8 km/h, increasing 1.2 km/h every minute while maintaining a constant 3% incline. Then, the main test started at 8.2 km/h with a constant 3% incline, and speed increased by 1.2 km/h every two minutes until exhaustion. The V-Slope method was used to measure VO₂ values at the anaerobic threshold. VO₂max was estimated based on three criteria: when the participant could not continue the test, when the VCO₂/VO₂ ratio exceeded 1.1, or when the maximum heart rate was reached with no more than a 10 beats/minute difference. To measure performance capacity, the countermovement jump (CMJ) technique was used, which involved jumping from a kneeling and hip-flexed position. Different parameters, such as maximum force, maximum velocity, maximum power, and level of developed force, were recorded. To assess lower limb speed and acceleration, the 40-meter linear acceleration test was employed, which demonstrated good reliability and validity.

Program of Corrective Foot Posture Exercises: In the experimental studies, the intervention group followed a 12-week exercise program aimed at correcting foot posture alterations, while the control group performed flexibility exercises. The exercises for the intervention group varied based on foot structural type (high or low) and focused on strengthening intrinsic and extrinsic foot muscles. The program was conducted under the supervision of an experienced physiotherapist. For participants with flat feet, exercises focused on strengthening the abductor hallucis, flexor digitorum brevis, and quadratus plantae muscles, with a progressive load over eight weeks. Additionally, myofascial release of the lateral long fibular muscle was performed. For participants with high arches, exercises emphasized improving flexibility of the tibialis posterior and gastrosoleus muscles. Strengthening exercises for the same muscles as in the flat feet group were also performed, with a gradual increase in load.

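### The exercise study has a control group, but its analysis names no programme-versus-control comparison, and the Friedman route cannot supply one

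*Combined protocol and SAP*

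**What the plan says.** The section on the corrective exercise programme gives the experimental studies two conditions: an intervention group does the 12-week programme, "while the control group performed flexibility exercises". Design and Sample reports "For the experimental studies, 33, 31, and 33 participants were selected" with low, high and neutral arches, and bases the sample size on "considering three independent groups, an alpha level set at 0.05", power 0.80 and f = 0.40. It does not say how the controls relate to these 97 athletes.

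The whole analysis of the programme is in the Statistical Analysis section:

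- Test: "the effects of exercise on dependent variables were assessed using repeated-measures ANOVA or Friedman's test".
- Follow-up: "Post-hoc analysis with Tukey correction was conducted to assess pre-post exercise significances of dependent variables".
- Effect size: partial eta-squared or, on the non-parametric route, "Kendall's W concordance coefficient was used to evaluate the effect size of the exercise program on foot types".

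For the descriptive studies the same section does state a between-group aim: "Post-hoc analysis with Bonferroni correction was performed to determine differences between groups". That sentence comes before the experimental text and belongs to the comparison of foot types. Among the specific objectives, the third seeks to establish that the exercises work, and the fourth seeks "possible improvements in sports performance resulting from the exercise program".

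**The concern.** A control group is useful only if the analysis compares it with the intervention group. No sentence names an intervention factor, a group-by-time interaction or a between-group comparison of change. What is stated is a pre-post assessment. A pre-post change mixes any programme effect with everything else that happens over 12 weeks, such as ordinary training, familiarity with the tests and regression to the mean. Measurements are taken in the general preparation phase of the sports semester, so a gain common to all athletes is plausible. Under the stated rule such a gain can be reported as an effect of the programme, with an effect size attached. This bears on the causal claim in two of the four specific objectives.

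**Working it through.** **1. What Friedman's test can compare.** It ranks the occasions within each athlete and sums the ranks over athletes. It has no between-subject factor. The groups of 33, 31 and 33 are independent athletes, not matched blocks, so the only factor available is time. This step needs no assumed figure.

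**2. What it becomes with two occasions** (assumed from the pre-post wording; no ties). If x of n athletes improve, Q = (2x − n)²/n on 1 degree of freedom, which is the large-sample sign test on change. Kendall's W = Q/n = (2x/n − 1)². Illustration: 24 of 33 improve with the programme and 24 of 33 improve in a control group of the same size.

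- Q = (48 − 33)²/33 = 225/33 = 6.818; p = 0.009.
- W = 6.818/33 = 0.21.

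Both groups give the same p and W. The effect size meant to describe the programme is as large in athletes who did not do it, and the between-group difference in the share improving is 0.

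**3. How often a programme with no effect looks effective.** Assume normal change scores and the same mean gain s in every group, in SD of change. The documents give no value for s, so a range is shown. For Friedman, the number improving is binomial with probability Φ(s), and the rejection rate is exact. For the paired t test, the noncentral t distribution with noncentrality s√n is used. The between-group rates come from 40,000 simulated studies of 33/31/33.

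| Shared gain s (SD of change) | 0.1 | 0.2 | 0.3 | 0.5 |
|---|---|---|---|---|
| Friedman, one group of 33 | 5% | 12% | 23% | 56% |
| Paired t, one group of 33 | 9% | 20% | 39% | 80% |
| Friedman, all 97 pooled | 11% | 32% | 62% | 97% |
| Kruskal-Wallis on change, or group-by-time F | 5% | 5% | 5% | 5% |

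**4. Informal use of the controls does not help.** Suppose low and high arches exercise, neutral arches are controls (assumed), and s = 0.3. The chance that at least one exercise group is significant while the control group is not is 36% with Friedman and 37% with paired t.

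**5. The plan's own sample-size inputs.** For a three-group one-way ANOVA with f = 0.40 and α = 0.05, the noncentral F with λ = Nf² gives power 0.798 at N = 63 and 0.818 at N = 66, so 66 athletes in equal groups are needed. The plan states no required N. With 97 athletes the power is 0.944; Kruskal-Wallis on normal change scores gives about 0.93. These figures apply to the programme question only if the three foot-type groups are the comparison and f is read as an effect on change. The plan says neither.

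**The case against.** The strongest reply concerns the parametric route. Repeated-measures ANOVA is the usual name for a model that may include a between-group factor, and three features suggest that one was intended: Levene's test is listed for the experimental studies and needs independent groups; the effect size refers to foot types; and the sizing is for three groups. Tukey could also be run over all group-by-time means. This is fair. For normal outcomes the defect is an unnamed contrast, and the paired t rates above apply only if no group factor was fitted. But foot type stands for intervention versus control only if the neutral-arch athletes are the controls, which no section says, and the stated purpose of the follow-up would still be pre-post.

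The error rates also rest on an assumed shared gain. At 0.1 SD, Friedman in one group of 33 rejects only 5% of the time, so little harm would follow. Pooling all 97, or comparing one group's p-value with another's, are analyses the plan does not describe; they are shown as possible readings. On detail, the exact sign test for 24 of 33 gives p = 0.0135 rather than 0.009, which changes nothing.

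Finally, objectives 3 and 4 begin by asking what changes after the programme, and a pre-post analysis answers that. It does not answer their claims that the exercises work or that improvements result from them.

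None of this touches the non-parametric route: no other part of the document supplies a between-group comparison of change for non-normal outcomes.

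**Conclusion.** The concern holds and must be fixed. For non-normal outcomes the stated test and effect size cannot compare programme with control; this is an error in the plan as written, not a missing detail. For normal outcomes the chosen model can make the comparison, but the plan does not name it and describes only a pre-post follow-up.

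The structural point rests on no assumption. Its size does: with no programme effect and a shared gain of 0.1 to 0.5 SD of change, a pre-post test in one group of 33 is significant in 5% to 56% of studies (Friedman) or 9% to 80% (paired t), against about 5% for a between-group test of change. These figures assume two occasions and normal change scores.

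**What to change.** In the Statistical Analysis section:

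1. Name the group-by-time term, that is, the between-group difference in pre-to-post change with its 95% CI, as the test of the programme.
2. For non-normal outcomes, replace Friedman and Kendall's W with Kruskal-Wallis, Mann-Whitney with a Hodges-Lehmann interval, or a permutation test, each on post-minus-pre change.
3. Make the post-hoc tests multiplicity-adjusted between-group contrasts of change, and label within-group pre-post p-values descriptive.
4. State how the controls relate to the 33, 31 and 33 athletes.
   - If arms were randomised within foot type, use ANCOVA of the post value on baseline, arm and foot type; for non-normal outcomes, permute arm within foot type. Relative to change scores, ANCOVA cuts the variance by (1 − r)/2: 35%, 25% or 15% at an assumed pre-post correlation r of 0.3, 0.5 or 0.7.
   - If the neutral-arch athletes are the controls, every contrast mixes programme with foot type and no test removes this. Say so, and conclude only that change differed between groups.

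The cost is one reworded paragraph and a re-run on the data collected (the plan's past tense suggests that they exist), with no new athletes. Some within-group improvements will no longer count as programme effects, and precision falls. In SD of change, the 95% CI half-width is 1.998 × √(1/33 + 1/33) = 0.49 for 33 v 33 and 0.50 for 31 v 33, against 2.037/√33 = 0.35 within one group of 33. The difference detectable with 80% power is 0.70 to 0.71 SD, or 0.77 to 0.79 SD with Bonferroni for two contrasts. If each foot type was split in half (assumed 17/16 and 16/15), it is 1.01 to 1.04 SD within a foot type, and the 97 athletes give much less information on the programme than the three-group power suggests.

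### The stated tests of the program effect use only athletes with both a pre-test and a post-test, and the plan names no analysis population or missing-data method for the rest

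*Combined protocol and SAP*

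**What the plan says.** The Statistical Analysis section gives one route for the experimental studies: "the effects of exercise on dependent variables were assessed using repeated-measures ANOVA or Friedman's test". The software is SPSS version 21. The follow-on comparison is pre-post: "Post-hoc analysis with Tukey correction was conducted to assess pre-post exercise significances of dependent variables".

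On the design, the corrective-exercise section says that "the intervention group followed a 12-week exercise program aimed at correcting foot posture alterations, while the control group performed flexibility exercises". The Design and Sample paragraph gives the numbers: "For the experimental studies, 33, 31, and 33 participants were selected, respectively, from a pool of 230 candidate athletes". For the cross-sectional part, "35 participants with low medial arch, 32 with high arch, and 36 with neutral arch were selected for the observational studies". The sample-size inputs are stated as "considering three independent groups, an alpha level set at 0.05, a power (1-β) of 0.80, and an effect size (f) of 0.40".

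The document does not state:
- an analysis population or an as-assigned rule;
- a method for missing measurements;
- an expected or observed drop-out rate, or an allowance for one in the sample size;
- whether athletes who stop the exercises are still tested at week 12;
- how the 97 athletes divide into intervention and control, or how they were allocated.

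**The concern.** Repeated-measures ANOVA in SPSS deletes cases listwise, and Friedman's test needs complete blocks. With two time points, an athlete without a post-test leaves the analysis entirely and the baseline already collected goes unused. The analysed set is then the completers, whether or not that was intended.

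This matters because objectives 3 and 4 ask whether a 12-week program changes stability, muscle activity and performance. The two arms do different work (strengthening with rising load against flexibility exercises), so equal or uninformative stopping cannot be taken for granted. Muscle-strength and postural-control tests also fall on different days. An athlete can therefore miss one post-test and not another, and the analysed set can change from outcome to outcome with nothing in the plan requiring that to be shown.

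**Working it through.** The plan has no drop-out or missing-data figure to reproduce. The stopping rates, pre-post correlations and stopping mechanisms below are assumptions.

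**Is loss a power problem?** One-way ANOVA, three groups, f = 0.40, alpha 0.05, noncentrality N × f²:
- N = 63 gives power 0.798 and N = 66 gives 0.818, so 66 are needed (22 per group).
- The experimental studies have 33 + 31 + 33 = 97, which gives 0.944.
- (97 - 66)/97 = 32% could be lost before that target is missed.

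This calculation is for three independent groups, not for the pre-post test. On the plan's own inputs, loss is mainly a question of bias.

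**Illustration 1: stopping depends on baseline, program arm only.** Write baseline as z in SD units, with pre-post correlation r and equal SDs at both times. The completers' mean change is the true change plus (r - 1) × m, where m is the mean z of those who stay. The bias is therefore -(1 - r) × m. With odds of stopping multiplied by 3 per SD lower baseline (log-odds slope 1.1):

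| Stopping | m | Bias, r = 0.7 | Bias, r = 0.5 |
|---|---|---|---|
| 6% | 0.061 | -0.02 | -0.03 |
| 15% | 0.142 | -0.04 | -0.07 |
| 25% | 0.228 | -0.07 | -0.11 |

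These values do not depend on the arm sizes. An estimator that keeps all baselines has bias of 0.005 SD or less in the same setting.

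- *Opposite direction.* If athletes with high baselines stop instead, the sign reverses. In a separate simulation with true effect 0.40 SD, 20% stopping and r = 0.7, completers gave 0.45 and the all-baselines estimator 0.40.
- *Both arms alike.* In that simulation, equal baseline-related stopping in both arms left the between-arm difference at 0.40, but the within-arm change was 0.45.
- *Unrelated stopping.* Completers gave 0.40, so there was no bias.

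**Illustration 2: those who stop gain nothing.** If a fraction p of the program arm stops with no gain and completers gain d, the effect over all who started is (1 - p) × d. The completers' figure is too large by 1/(1 - p):
- p = 0.06: 1/0.94 = 1.06, or +6%
- p = 0.15: 1/0.85 = 1.18, or +18%
- p = 0.25: 1/0.75 = 1.33, or +33%

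**Does keeping all baselines repair this?** Barely, when stopping follows benefit. With true effect 0.40 SD, 20% stopping, r = 0.7 and less benefit making stopping more likely, completers gave 0.53 and the all-baselines estimator 0.52.

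**The case against.** The strongest reply is that nothing shows anyone stopped. If all 97 have both tests, the methods lose nobody. That is correct, and it is why no bias can be attributed to this trial from the document.

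Three stronger readings are tempting and are not supported:
- *The fall from 103 to 97 athletes (6/103 = 5.8%) is attrition.* Both are given as numbers selected. Nothing says that the 97 are the 103 after losses.
- *Athletes who stop are not re-measured.* The document is silent on this, which does not establish that it was so.
- *The low- and high-arch athletes (33 + 31 = 64) form the program arm and the 33 neutral-arch athletes the control.* The plan mentions an intervention and a control group but gives no split.

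It can also be said that the baseline-related bias is modest. With 97 athletes in near-equal arms (48 and 49, assumed), the standard error of the difference in change is √[2(1 - r)(1/48 + 1/49)], or 0.16 SD at r = 0.7 and 0.20 SD at r = 0.5. The bias at 25% stopping is about half of that or a little more. This stands, and so does the point that the two illustrations run in opposite directions.

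Finally, a completers' effect is a legitimate target if labelled as such, and objectives 3 and 4 speak of changes after the program. But objective 3 also claims effectiveness, and the plan does not say that completers are its target.

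**Conclusion.** The point holds as a defect of the stated method. The only analyses named for the program effect drop every athlete without both tests, and the document supplies nothing to cover those athletes.

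Any bias in this trial is of unknown size and direction. The ranges of -0.02 to -0.11 SD and +6 to +33% rest on assumed stopping of 6 to 25%. The first also assumes low-baseline stopping confined to the program arm with correlation 0.5 to 0.7, and the second that those who stop gain nothing. There is no bias if nobody stopped or if stopping was unrelated to baseline and benefit. It should be corrected because the remedy is cheap and a reader cannot otherwise tell which case applies.

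**What to change.** 1. Replace repeated-measures ANOVA with a linear mixed model (group, time, group × time; SPSS MIXED). Include every athlete with at least one measurement, in the group first assigned. Since no allocation method is described, this keeps everyone in but does not by itself make the comparison a randomised one.
2. Where the plan would switch to Friedman's test, keep the same model and use a transformation or a bootstrap.
3. Where testing is still under way, seek the week-12 measurement from athletes who stopped, if they are able to be tested. The text is largely in the past tense, so this may no longer be possible; the other steps need only existing data.
4. Report numbers started, stopped and re-tested, by arm and foot type, and say what the 97 represents.
5. Show the completers-only result as a sensitivity analysis.
6. State that the mixed model corrects stopping related to observed baseline but not stopping related to unobserved benefit. For the latter, add a sensitivity analysis assuming no change in athletes without a post-test.

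The cost is a few sentences of analysis text, a flow table and slightly more analysis work. The reported effect may come out smaller than the completers' effect.
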